	Episodic Memory – Picture Sequence Memory Test (Bauer et al., 2013; Dikmen et al., 2014)			
	GL al., 2014)			
	Language – Oral Reading Recognition Test			
	Language – Picture Vocabulary Test (Dunn & Dunn, 1981)			
	Processing Speed – Pattern Comparison Processing Speed Test (Carlozzi et al., 2014)			
	Working Memory – List Sorting Working Memory Test (Weintraub et al., 2013)			
	Dexterity – 9-hole Pegboard Dexterity Test (Wang, Bohannon, Kapellusch, Garg, & Gershon, 2015)			
	 Strength – Grip Strength Test (Hamilton, Balnave, & Adams, 1994)			
	odoligin - Olip odoligin rest (riaminton, Dalliave, & Adams, 1994)			

PROMIS measures self-report of emotional functioning (Cella et al., 2007)

Each test in this panel is age normed. Therefore even though subjects will be of different ages, the change in their performance as a percentage of the normed values will be relevant and comparable from subject-to-subject. There are also published test-retest standard deviations from which to ascertain how much of a change in score is needed for a change to be regarded as significant.

Secondary Outcome Measures:

Secondary outcome measures include: change in quantitative EEG (power asymmetry), SWS clinical neuroscore, and birthmark score.

Another secondary outcome measure will be an assessment of impact upon seizures. Parents/caregivers will report the following before starting study drug and at each visit:

- Number of seizures (specifically motor seizures) This is the most reliable and important seizure outcome.
- Seizure duration
- Seizure Type
- Number of episodes of status epilepticus, defined as generalized convulsive seizure lasting longer than 10 minutes
- Number of uses of rescue medication.
- Number of ER visits/ hospitalizations for seizures

Statistical Considerations (sample size and analysis plan):

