Results of the above tests will be compared to age normed values. In addition, the difference in results between final test results and initial test results will be obtained for the cognitive functioning score of each subject. Mean and standard deviation of this difference for all 10 subjects will be calculated. These results will be used to determine whether individuals and the group as a whole demonstrated age normed changes in their cognitive functioning over the course of the six month trial. Neuropsychological testing will occur at both sites, KKI and CCHMC, and the deidentified results will be sent to KKI for analysis. There is no control group in this study of subjects who are not receiving study drug. The published test-retest standard deviations will be used to determine whether changes in testing results exceed expected test-retest changes in results.

Expected seizure rate can vary greatly both between subjects and for an individual. Subjects must be on the same AEDs for the past three months to join the study. Subjects whose seizures increase to the point where it is necessary to add another seizure medication, start the ketogenic or Atkins diet, or go for surgery to control their seizures will be removed from the study.

Quantitative EEG: An EEG will be done prior to starting study drug and at the end of the study while still on study drug. An asymmetry in power (roughly an integration of amplitude and frequency) in the affected side of the brain compared to the unaffected (or less affected) side of the brain, will be quantified as previously described (Hatfield et al., 2007; Ewen et al., 2009) for the quantitative EEG analysis. EEGs will occur at both sites, KKI and CCHMC, and the de-identified EEGs will be sent to KKI for analysis. The reason for this analysis is as a non-invasive biomarker of brain function which could be useful to develop as a marker of drug response. Quantitative EEG power analysis reflects an integration of the EEG activity amplitude and frequency. Therefore asymmetry of power on qEEG for these subjects reflects the increased slowing and decreased amplitude frequently seen in these patients interictally as their neurologic involvement progresses. Even patients with bilateral brain involvement have more involvement on one side than on the other side. Power asymmetry on qEEG has been shown to correlate with brain perfusion, brain atrophy, and SWS neuroscore, therefore, it has the potential as a biomarker responsive to

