5.9 Quality Control: Study Related Procedures

- 1. Clinical coordinators at both sites will review the case report forms after completion by [name] or [name] to resolve any issues.
- 2. [name] and [name] will review the study progress regularly with monthly phone conferences. The two sites will have internal reviews performed regularly to ensure high quality of the study procedures and subsequent data.
- 3. The DMCC will perform an audit of the overall protocol including this pilot project.

6. Statistical Considerations

The proposed trial is a pilot drug trial. Based on the results, a sample size calculation will be done, using the cognitive outcome with the greatest response to the study drug, to plan a follow up randomized, placebo-controlled trial, should one be warranted. If no serious adverse events which are thought to probably or possibly be due to the study drug AND the cognitive data suggests a trend for possible benefit, then the results of this study will be used to plan a larger follow-up clinical trial.

Children and adults between 3 and 31 years of age with Sturge-Weber syndrome brain involvement and cognitive impairments will be eligible for this pilot study. A total of 10 patients will be enrolled at two centers including Cincinnati Children's Hospital Medical Center and the Kennedy Krieger Institute. This sample size was selected based on 1) availability of potential appropriate subjects at both centers and 2) upon the investigators experience with similar clinical trials.

Cognitive tests proposed have been previously validated in the literature and are normed to aged matched normal controls. These are published tests which are widely used. Therefore, responders in this trial will be subjects whose normed results improve on the task more than what is expected for the increase in age (6 months) +/- expected standard deviation.

Anticipated number of patients to be enrolled:

Table 4

	American Indian or Alaskan Native	Asian or Pacific Islander	Black, not of Hispanic Origin	Hispanic	White, not of Hispanic Origin	Other or Unknown	Total
Female	0	1	1	0	3		5
Male	1	0	0	1	3		5
Total	1	1	1	1	6		10

7. Data Management

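### Cognitive responders are judged against published test-retest SDs that probably do not describe untreated SWS patients, and only improvers are counted

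*Combined protocol and SAP*

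**What the plan says.** The Protocol Synopsis, under Primary Outcome Measures, introduces the yardstick: "There are also published test-retest standard deviations from which to ascertain how much of a change in score is needed" before a change is called significant. Section 5.3 (Laboratory tests and clinical procedures) repeats this. The Statistical Considerations part of the Synopsis states "There is no control group in this study of subjects who are not receiving study drug", and then: "The published test-retest standard deviations will be used to determine whether changes in testing results exceed expected test-retest changes in results". For the group it says "Mean and standard deviation of this difference for all 10 subjects will be calculated", and that these results will decide whether individuals and the group changed. No interval, test or significance level is attached to cognitive change.

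Section 6 says: "Cognitive tests proposed have been previously validated in the literature and are normed to aged matched normal controls". It defines responders as subjects "whose normed results improve on the task more than what is expected for the increase in age (6 months) +/- expected standard deviation". Subjects who get worse by the same amount have no counterpart category.

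The population is set in Section 4.1, which requires a cognitive neuroscore of at least 1. Section 3 reports that only about a third of an SWS cohort had an IQ in the normal range. Section 4.6 schedules neuropsychological testing twice: once before drug and once at six months.

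**The concern.** In a single-arm trial something has to stand in for what would have happened without drug. Here, for the individual responder call, that stand-in is the published test-retest SD. If it comes from ordinary test-takers, a change beyond it says only that the subject moved more than an ordinary person does on retest. The question of interest is whether the subject moved more than a cognitively impaired SWS patient would have moved over six months off drug. The documents carry no SWS retest SD, and with one pre-drug assessment the trial cannot estimate one.

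If untreated SWS patients vary more than the published samples, ordinary fluctuation crosses the cut-off more often. It does so in both directions, but the responder definition looks at one direction only, so a bare responder count can read noise as benefit. Under Section 6 a trend towards cognitive benefit is one of two conditions for planning a larger trial, and the cognitive outcome with the greatest response is used to size it. A test that happens to be noisier in SWS would tend to look more responsive.

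**Working it through.** The plan gives no SD, effect size, significance level or power for the cognitive outcome, and n=10 is justified by availability and experience, so there is no stated figure to reproduce. What follows is an illustration.

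**Inputs**
- n = 10 (Section 6).
- Cut-off c = 1 published SD above expectation. This is the literal reading of the Section 6 responder definition, taking its expected standard deviation to be the published test-retest SD. No multiple is stated anywhere.
- k = untreated SWS SD of change divided by published SD. **Assumption:** range 1 to 2; not in the documents.
- No drug effect, and changes normally distributed around the age expectation (assumption).

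**False responder per subject per task:** P = 1 − Φ(c/k), with c = 1.

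| k | 1/k | P(false responder) | Expected among 10 | Chance of 3 or more of 10 |
|---|---|---|---|---|
| 1 | 1.000 | 16% | 1.6 | 20% |
| 1.3 | 0.769 | 22% | 2.2 | 39% |
| 1.5 | 0.667 | 25% | 2.5 | 48% |
| 2 | 0.500 | 31% | 3.1 | 64% |

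The last column is the upper binomial tail with 10 subjects.

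**What belongs to the SD and what to the multiplier.** At k=1 the borrowed SD is exactly right and the rule still labels 16% of subjects as responders. Only the excess is due to the SD: 22 − 16 = 6 points at k=1.3, 25 − 16 = 9 at k=1.5 and 31 − 16 = 15 at k=2. If k were below 1 the rate would fall; at k=0.8, 1 − Φ(1.25) is about 11%.

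**Group mean.** An interval built on the subjects' own SD of change already absorbs zero-mean fluctuation, whatever k is. In simulation (n=10, 200,000 runs, no effect) a two-sided 5% one-sample t-test on that SD rejected in 4.9% to 5.1% of runs at k = 1, 1.5 and 2. The half-width of the 95% interval is 2.262 × SD/√10 = 0.72 SD. The multiplier 2.262 (9 df) is about 15% larger than 1.96.

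**Decliners as a check, and its limit.** If untreated changes are symmetric about the expectation, improvers and decliners beyond the same cut-off are equal in expectation for every k. A mean shift breaks this. With a practice gain of +0.5 published SD and k=1.5:
- improvers: 1 − Φ((1 − 0.5)/1.5) = 1 − Φ(0.333) = 36.9%
- decliners: 1 − Φ((1 + 0.5)/1.5) = 1 − Φ(1.0) = 15.9%

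That is a net 21 points with no drug effect. A natural decline of the same size reverses the two figures.

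**The case against.** The strongest reply is that several steps are inferred. The documents say the norms come from normal controls; they do not say which sample produced the retest SDs. Nothing in them measures cognitive variability in SWS. The nearest statement, "Expected seizure rate can vary greatly both between subjects and for an individual", concerns seizures, and entry requires stable anti-epileptic drugs and the ability to be tested, which may limit fluctuation. So neither k>1 nor its size is established. That stands. It leaves the reference unverified rather than shown to be wrong.

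Three stronger readings are tempting and are not supported:
- **That the group analysis is a test with an inflated error rate.** No cognitive hypothesis test is specified, and the Synopsis ties the group judgement to the observed mean and SD. Error rates for a z-test scaled by the published SD would describe a procedure the plan does not contain. What remains open is that no interval is attached and the text does not say which SD decides.
- **That modest extra variability doubles the false-responder rate.** At the literal 1-SD cut-off it goes from 16% to 31% over the whole assumed range and does not double. Doubling near k=1.3 needs a 1.645-SD cut-off, which the plan never states.
- **That the go decision rests on a responder count.** Section 6 asks for a trend towards possible benefit and names no count, and the mean change does include decliners.

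It is also fair that this is a ten-subject pilot which says openly that it has no controls and is meant to lead to a randomized placebo-controlled trial. That limits the consequence, but the responder result can still shape that trial's primary outcome and size.

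**Conclusion.** The point holds in limited form. The published test-retest SD is the only external yardstick for cognitive change, its source sample is not named, and it probably does not describe untreated, cognitively impaired SWS patients retested at six months. Exceeding it cannot be read as exceeding untreated SWS change, and counting improvers alone lets noise appear as benefit.

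Under the literal 1-SD rule the chance of a false responder per task runs from 16% (k=1) to 31% (k=2), of which 0 to 15 points are due to the SD and the rest to the multiplier. This rests on an assumed k, normal changes and no mean shift; the documents fix none of these. The group summary is not shown to be inflated. It lacks an interval and a clear statement of which SD governs.

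**What to change.** Change the wording of the Synopsis (Statistical Considerations) and Section 6:

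1. **Group level.** State that the conclusion for each test rests on the mean change with a 95% t-interval from the subjects' own SD of change (9 df if all ten are analysed). Keep the published SD as a descriptive reference only, and name its source sample, retest interval and the multiple used.
2. **Individual level.** Report the number of subjects who decline beyond the same cut-off next to the number who improve, and do not read improvers alone as response.
3. **Language.** Describe the results as change on drug, not drug response. Items 1 and 2 deal with spread only; neither separates a drug effect from a mean practice gain or natural change.

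Cost: text changes and one more column in the responder table, with no new data or visits. The SD of change is already to be calculated. The downside is an interval wider than one that treats the SD as known, and a less favourable net responder figure.

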of warfarin or on a stable dose of LMW heparin for >2 weeks.)
of warfarin or on a stable dose of LMW heparin for >2 weeks.) 9. Adequate liver function as shown by:
of warfarin or on a stable dose of LMW heparin for >2 weeks.)

- 10. Written informed consent according to local guidelines. Local guidelines for subject assent will also be followed.
 11. Stable dose of medications affecting the cytochrome P 450 3A4 (CYP3A4) and p glycoprotein (P gp) systems for at least 3 months prior to consent.

Treatment				
Agent-	Rapamune® / Rapamycin® (sirolimus)			
Dosage,	Oral dose targeting a serum level dose range of 4-6 ng/mL given for a minimum of			
schedule, route of	six months. Dose based on surface age, surface area, and mini-PK as outlined in			
administration-	the protocol.			
	Subjects will receive no more than 2 mg/day given in two divided doses for a			
1	minimum of six months with the option to enter into the Extension Phase up to an			
	additional year and a half.			
Primary	Safety and Tolerability of sirolimus in patients with Sturge-Weber syndrome.			
Outcome	Adverse Events will be determined at every visit and on every phone call			
Measures:	using a case report with a list of side effects which can be seen with higher			
	doses and serum levels than are expected with this study. Impact of the			
	study drug upon seizure frequency, type, and duration will be assessed by			
	patient/parent report using a seizure report form we have used in a prior study. Impact of study drug upon neurologic, ophthalmologic, endocrine,			
	medical rehab, and dermatologic status will be assessed with case report			
	forms, the physical exam, the Sturge-Weber syndrome neuroscore, the port-			
	wine birthmark score, and other outcome measures described in the			
	protocol.			
	Change over six months in cognitive functioning in Sturge-Weber syndrome			
	is the primary outcome measure. This outcome will be assessed using a			
	panel of testing selected based upon extensive experience in testing			
	cognitive function in adults and children with SWS at the Kennedy Krieger			
	Sturge-Weber Center. These will include the following measures from the			
	National Institute of Health Toolbox (Gershon et al., 2010):			
	Attention/Executive Function – Flanker Inhibitory Control and Attention Test (Eriksen & Eriksen, 1974)			
	Executive Functioning – Dimensional Change Card Sort Test (Zelazo, Frye, & Rapus,1996)			

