monitor sirolimus treatment, both from the standpoint of safety and efficacy in a future larger clinical trial.

Seizure (motor seizures) number will be collected at each study visit and compared across visits. Seizure number will be recorded from the two months prior to joining the study at baseline (by history) and "since last visit" for all study visits. Seizure length and type, need for rescue medication, ER visit or hospitalization will also be recorded and compared across visits and at the end of the study (on drug) compared to the beginning of the study (prior to starting drug). There will be stopping rules for safety.

Clinical neurologic severity scores (neuroscores) will be collected at each study visit, using a scale developed and validated by KKI. The neuroscore is comprised the frequency of seizures, extent of hemiparesis, assessment of visual field cut, and degree of cognitive functioning with a total score of 15 possible (Kelly, Hatfield, Lin, & [name], 2005). Descriptive statistics for this measure will be reported in the form of median and range. Mann Whitney U Test will be used to assess whether a significant change in neuroscores has occurred after treatment compared to prior to treatment. Neuroscores will be collected at both sites, KKI and CCHMC, and the de-identified results will be sent to KKI for analysis.

The Neurologic Quality of Life (Neuro QoL) will be collected prior to starting study drug and at each study visit. Descriptive statistics for this measure will be reported in the form of median and range. Mann Whitney U Test will be used to assess whether a significant change in quality of life has occurred after treatment compared to prior to treatment. NeuroQoL will be collected at both sites, KKI and CCHMC, and the deidentified results will be sent to KKI for analysis.

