The quantification of the facial birthmark score developed and validated at the KKI will occur at the beginning of the study, prior to starting study drug, and when the subjects reach the endpoint of the study at six months' time while still on study drug (Waelchli et al., 2014). If the subject elects to enter the Extension Phase, the facial birthmark will be rated at each Extension Phase visit. Descriptive statistics for this measure will be reported in the form of median and range. Mann Whitney U Test will be used to assess whether a significant change in the facial birthmark has occurred after treatment compared to prior to treatment. Facial birthmark scoring will occur at both sites, KKI and CCHMC, and the de-identified results will be sent to KKI for analysis.

Biomarker Development: Spearman's rho will be used to assess for the strength, direction and significance of correlations between qEEG results and neuropsychological outcomes, NeuroQoL and the SWS Neuroscore. Significance will be taken at p<0.05.

All of these outcomes will be used to determine whether sirolimus is 1) sufficiently well tolerated in this small group of subject and 2) what outcome measures and biomarkers demonstrate preliminary evidence of being responsive to sirolimus. This information will be used to determine the advisability of proceeding with a larger multicentered study and aid in the selection of outcome measures and biomarkers to be part of that follow-up randomized placebo-controlled trial.

Sponsors (federal, state, foundation and industry support): National Institute of Health (NIH) Faneca 66 Foundation

Pfizer (study drug only)

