Frequency and	above (approximately 0.2 to
Timing:	0.5, clinical doses adjusted for body surface area). Embryo/feto toxicity was manifested as mortality and reduced fetal weights (with associated delays in skeletal ossification). Sirolimus is excreted in trace amounts in milk of lactating rats. It is not known whether sirolimus is excreted in human milk.

(L) Toxicity may also occur later.

Laboratory tests and clinical procedures:

- Weight and vitals will be monitored at baseline and at each visit.
- As part of the current medical history assessed at each visit, patients will be screened for any change in their physical functioning.
- Neuroscores will be assigned at each visit by [name] or [name]. Neurologic exam and general physical exam will also be done at each visit.

Clinical neurologic severity scores (neuroscores) will be collected at each study visit, using a scale developed and validated by KKI. The neuroscore is comprised of the frequency of seizures, extent of hemiparesis, assessment of visual field cut, and degree of cognitive functioning with a total score of 15 possible (Kelly, Hatfield, Lin, & [name], 2005). Descriptive statistics for this measure will be reported in the form of median and range. Mann Whitney U Test will be used to assess whether a significant change in neuroscores has occurred after treatment compared to prior to treatment. Neuroscores will be collected at both sites, KKI and CCHMC, and the de-identified results will be sent to KKI for analysis.

Seizure severity will be assessed at each visit by [name] or [name].

Parents/caregivers will report the following before starting study drug and at each visit to assess the impact of sirolimus upon seizures:

- Number of seizures (specifically motor seizures) This is the most reliable and important seizure outcome.
- o Seizure duration
- Seizure Type
- Number of episodes of status epilepticus, defined as generalized convulsive seizure lasting longer than 10 minutes
- Number of uses of rescue medication
- Number of ER visits/ hospitalizations for seizures
- Patients will be asked at each clinic visit or phone interaction about migraine frequency and severity and any change in neurologic symptoms.

 Frontal and profile photograph will be taken under standardized conditions with scoring of the port-wine birthmark for percent of face covered, thickness of birthmark, and darkness of birthmark color.

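### Motor seizure counts covering about 8.7 weeks before drug and 2, 3, 9 and 12 weeks on drug are compared across visits without conversion to a rate

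*Combined protocol and SAP*

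**What the plan says.** The seizure analysis is in the Protocol Synopsis, under Statistical Considerations: "Seizure (motor seizures) number will be collected at each study visit and compared across visits". The pre-drug value is defined there as follows: "Seizure number will be recorded from the two months prior to joining the study at baseline (by history"). For all study visits the count runs from the previous visit. Rescue medication, emergency visits and hospitalizations are also compared across visits.

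The Synopsis (Secondary Outcome Measures) ranks this item first among the seizure measures: "Number of seizures (specifically motor seizures) This is the most reliable and important seizure outcome". Section 5.3 (Laboratory tests and clinical procedures) repeats the list without a time unit: "Parents/caregivers will report the following before starting study drug and at each visit to assess the impact of sirolimus upon seizures". The Schedule of Events (section 4.6) puts Visits 1 to 7 at weeks -2, 0, 2, 5, 14, 26 and 38, with a seizure history at each. Section 5.3 starts study drug at Visit 2.

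Two places use time-based words. Primary Outcome Measures refer to the impact of "study drug upon seizure frequency, type, and duration will be assessed by" patient or parent report. Statistical Considerations remark: "Expected seizure rate can vary greatly both between subjects and for an individual". Neither defines a rate or a denominator. Section 6 does not mention seizures.

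**The concern.** A count rises and falls with the length of time over which it is taken. Here that length differs between baseline and every on-drug visit, and among the on-drug visits themselves. Comparing the numbers as they stand therefore builds in a pattern unrelated to the drug: an apparent early improvement, then a climb as the visit gaps lengthen. A real reduction late in the study can be hidden.

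There is no control group to show the same artefact and no named test for seizure counts, so the comparison of counts is the whole analysis of this outcome. It contributes to the overall judgement in the Synopsis: "All of these outcomes will be used to determine whether sirolimus is 1) sufficiently well tolerated in this small group of subject". The same paragraph uses the outcomes to choose measures for the follow-up trial. The reach is limited, however. The rule in section 6 for planning a larger trial rests on drug-related serious adverse events "AND the cognitive data suggests a trend for possible benefit", and seizure number is not part of it.

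**Working it through.** The plan states no seizure rate, effect size or test for this outcome, so there is no figure of its own to reproduce. The check is arithmetic on interval lengths.

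**Inputs**
- Baseline period: two months (Synopsis, Statistical Considerations) = 2 × 365.25 / 12 / 7 = 8.696 weeks.
- On-drug visits 3 to 6: weeks 2, 5, 14 and 26, with drug started at week 0 (sections 4.6 and 5.3).
- Intervals: 2 - 0 = 2, 5 - 2 = 3, 14 - 5 = 9, 26 - 14 = 12 weeks.

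**Expected change at a constant nonzero rate**

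Expected count = rate × weeks covered, so the ratio to baseline is interval / 8.696 whatever the rate.

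| Visit (week) | Weeks covered | Ratio to baseline | Apparent change |
|---|---|---|---|
| 3 (2) | 2 | 0.230 | -77.0% |
| 4 (5) | 3 | 0.345 | -65.5% |
| 5 (14) | 9 | 1.035 | +3.5% |
| 6 (26) | 12 | 1.380 | +38.0% |

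Equal counts at baseline and week 26 imply a true fall in rate of 1 - 8.696/12 = 27.5%.

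**Meaning of two months.** At 59 days the week 26 figure is +42.4%, and at 62 days +35.5%. Read as 8 weeks, the four figures are -75.0%, -62.5%, +12.5% and +50.0%.

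**Visit windows.** The window row in section 4.6 is broken in the text available, so its reading is an assumption. With Visit 2 fixed, ±7 days at Visits 3 to 5 and ±14 days at Visit 6:

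| Visit | Weeks covered | Apparent change |
|---|---|---|
| 3 | 1 to 3 | -88.5% to -65.5% |
| 4 | 1 to 5 | -88.5% to -42.5% |
| 5 | 7 to 11 | -19.5% to +26.5% |
| 6 | 9 to 15 | +3.5% to +72.5% |

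The masked fall at Visit 6 then runs from 1 - 8.696/9 = 3.4% to 1 - 8.696/15 = 42.0%.

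On the widest reading, ±14 days at every visit including Visit 2, the longest gaps to Visits 3 and 4 are 2 + 4 = 6 and 3 + 4 = 7 weeks. Both are still shorter than 8.696. The gap to Visit 6 becomes 12 ± 4 = 8 to 16 weeks, or -8% to +84%.

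**Absolute size.** The documents give no seizure rate. Assuming 0.5, 1, 4 or 8 seizures per 28 days (count = rate × weeks / 4), expected counts at an unchanged rate go from 1.1 to 1.5, 2.2 to 3.0, 8.7 to 12, or 17.4 to 24 between baseline and week 26. A subject with no seizures shows no artefact.

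**Early removal.** Section 5.7 has a subject removed for loss of seizure control complete the ending assessments. Suppose, as an illustration, that this happens 4 weeks after the last visit with the rate doubled. The expected count is 2 × 4 / 8.696 = 0.92 of baseline, so a clear worsening would read as a slight fall.

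**The case against.** The best reply is that the plan never says the counts will be left unadjusted. It is silent, and there are signs that its authors think in rates:
- The primary outcome text speaks of frequency and refers to a report form from a prior study that is not in the documents.
- Section 5.7 defines loss of seizure control partly by frequency.
- The neuroscore, compared before and after treatment, includes seizure frequency.
- Section 5.0 gives the expected adverse event rate per subject per month.

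The consequences are also modest. No test, threshold or responder rule uses the count, and removal for seizures depends on the need for a new treatment. A reader who knows the schedule would see at once that a two-week count is smaller than a two-month one.

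Much of this stands as a limit on the consequences. A rate may well have been meant, and no false-positive rate can be claimed. But the only sentence that describes the comparison names number as the variable. The neuroscore is a composite and does not replace it. The adverse event figure shows that the authors write down a rate when they use one. The week 26 distortion is also less obvious to a reader than the early one, and two analysts could report opposite directions there from the same data.

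**Conclusion.** The concern holds. Following the plan's wording puts a schedule-driven pattern into its leading seizure measure: nominally -77.0%, -65.5%, +3.5% and +38.0% from baseline at weeks 2, 5, 14 and 26 with no change in rate. The early apparent fall does not depend on how the windows are read. The week 26 rise does: it is +38.0% at the nominal weeks, nearly vanishes at the short end of the assumed windows, and could reverse under the widest ones. The week 14 count is close to comparable. The percentages assume a constant nonzero rate; the absolute counts depend on a seizure rate that the plan does not give.

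This should be corrected before analysis because it affects a safety-related secondary outcome and the choice of measures. It does not touch the cognitive outcome, the sample size of 10 or the section 6 rule.

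**What to change.** In Statistical Considerations, define the variable as motor seizures per 28 days = count / actual days covered × 28. State that the comparison is within subject and that the two-month pre-drug rate is the reference. State the number of days taken for that period, since it is collected by history (two months = 2 × 365.25 / 12 = 60.9 days). Say also how any Visit 2 count is used: it would be a second pre-drug value covering about 2 weeks.

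Apply the same scaling to rescue-medication uses, status epilepticus episodes and emergency visits or hospitalizations where they are counted over the same intervals. Show the days covered beside each rate, because scaling removes the distortion but not the imprecision of a 2- or 3-week count. A count model with log observation time as offset would serve equally well.

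At an unchanged rate the expected ratio to baseline is then 1.00 at every visit. The cost is one or two sentences for the core definition and a line for the Visit 2 count. It uses visit dates and needs no new data, visits or clinical rules.
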